We propose a pilot clinical trial on the use of perioperative pregabalin in order to decrease ureteral stent related symptoms and decrease opioid usage after ureteroscopy with stent placement. Patients undergoing ureteroscopy with stent placement will receive a single dose of 300 mg pregabalin PO in the preoperative area. We will assess safety and feasibility of studying this regimen at our institution, with the aim of performing a randomized, placebo-controlled, double-blinded study in the future.

OBJECTIVES AND SCIENTIFIC AIMS

Primary Hypothesis

It is safe and feasible to study perioperative pregabalin in ureteroscopy with stent placement at our institution.

Exploratory Hypotheses

We hypothesize that the use of the perioperative pregabalin will:

- decrease ureteral stent related symptoms at 3 days post-op
- decrease the probability of a patient requiring narcotic pain medication
- decrease the total amount of narcotic pain medication used
- decrease the unplanned contact between the patient and the healthcare system related to the stent
- improve patient satisfaction after ureteroscopy with stent placement

Primary Endpoints

The primary endpoints will be as follows:

- Adverse events related to study drug
- Verified correct administration of study drug
- Correct use of study instruments

Secondary Endpoints:

Secondary endpoints include the following:

- Ureteral Stent Related Symptom Questionnaire (USSQ) [1] score at 3 days post op
- Monitored prescribing of narcotic pain medication
- Number of patients taking narcotic pain medication at several time points
- Oral morphine equivalents the patient has used at several time points
- Number of unplanned contacts between the patient and the healthcare system within 30 days
- Score on standardized evaluation of patient satisfaction

BACKGROUND AND STUDY DESIGN/INTERVENTION

The prevalence of urolithiasis is greater than 8% and increasing in the United States (US) [2]. There are several treatment options, including ureteroscopy (with or without laser lithotripsy), extracorporeal shock wave lithotripsy, and percutaneous nephrolithotomy. A recent study in California demonstrated that ureteroscopic treatment was employed in more than 40% of interventions [3], with some nationwide estimates up to 59% [4]. At least 300,000 stone

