We propose a study to extend the literature base on the use of perioperative pregabalin to ureteroscopy with stent placement through a prospective, randomized controlled trial. In order to ensure safety and feasibility of this future study, we will first perform a small pilot. We will administer study medication and study questionnaires. There will be additional components of study evaluation. This will be used to inform the design of a future trial.

CRITERIA FOR SUBJECT ELIGIBILITY

Subject Population

Undergoing elective ureteroscopy with stent placement by [name] at University of Missouri Hospital and affiliated facilities

Subject Inclusion

Age \geq 18 years

Subject Exclusion

- Renal insufficiency (eGFR $<$ 30 mL/minute/1.73 m²)
- Chronic indwelling ureteral stent
- Chronic opioid use
- History of opioid abuse
- Chronic gabapentinoid use
- Plan for inpatient hospitalization
- Pregnancy
- Inability of the patient to consent for themselves in English
- Allergy to gabapentinoid
- Liver failure or hepatic dysfunction

OVERVIEW OF STUDY DESIGNATION

Design

This is a pilot clinical trial on the use of perioperative pregabalin in order to decrease ureteral stent related symptoms and decrease opioid usage after ureteroscopy with stent placement. Patients undergoing ureteroscopy with stent placement will receive a single dose of 300 mg pregabalin PO in the preoperative area.

Pre-op standardized care

After obtaining written consent, patients will be enrolled. All patients will be told the following by a member of the study staff:

“We will be administering several medications before, during, and after your procedure to help with pain. We expect that you will be able to go home with just non-steroidal pain medication.” They will also be counseled on the risks and benefits of non-steroidal anti-inflammatory drugs (NSAIDS).

Subsequently, all patients will be given a single dose of pregabalin 300 mg PO with a sip of water approximately one hour before surgery. This will be administered per standard institutional practice. It will be recorded in the regular medical chart of the patient.

Post-op standardized care

Perioperative care, surgery and anesthesia, for all subjects will be per standard hospital protocol.

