This study does not require any additional pretreatment evaluations other than those which are part of current clinical care standards for a patient undergoing ureteroscopy with stent placement at University of Missouri. Preoperative evaluations typically include the following:

- Routine history and physical examination to include documentation of any comorbidities, medications (including complementary and alternative medications), family history, social history (alcohol and tobacco usage), height, body weight
- Past medical history including previous treatment for addiction
- Past surgical history including other uses of stents in the patient's lifetime
- Evaluation of renal function
- Any woman of child bearing age who believes she may be pregnant receives a pregnancy test

SURGICAL PLAN

The technique of surgery will have been determined to be ureteroscopy with stent placement based on the discretion of the surgeon and patient. None of the techniques utilized in the study are considered experimental and all are considered standard therapeutic options for patients with

indications for this procedure. Typical indications include nephroureterolithiasis and evaluation for malignancy.

The operating team will consist of surgeons on faculty at University of Missouri Department of Surgery-Urology Division. The procedures are performed under standardized general anesthesia with standard intraoperative vital sign monitoring.

EVALUATION DURING TREATMENT/INTERVENTION

Not part of usual care

This protocol requires several evaluations outside those typically used. These are all questionnaires.

Timing	Questionnaire	Respondent
Day of surgery	Screening questionnaire	Study staff
	Baseline surgery	Patient
	Post-op surgeon	Treatment staff
	PACU	Patient/PACU nurse
	Aldrete	PACU nurse
	Evaluation of trial	Patient
	Evaluation of trial	PACU nurse
	3 days post op	Early patient questionnaire
	USSQ	Patient
	Evaluation of trial	Patient
7 days post op	Early patient questionnaire	Patient
	Evaluation of trial	Patient
30 days post op	30 days post op study	Study staff
	Late patient questionnaire	Patient
	Evaluation of trial	Patient
	90 days post op	Late patient questionnaire
	Evaluation of trial	Patient
	6 months post op	Late patient questionnaire
	Evaluation of trial	Patient
	1-year post op	Late patient questionnaire
	Evaluation of trial	Patient
	Untimed	Unanticipated contact
	Evaluation of trial	Patient

Usual care

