Routine evaluation and management for those undergoing ureteroscopy with stent placement include:

ASA classification, assigned by the anesthesiologist

Deep venous thrombosis prophylaxis per standardized pathway

Estimated blood loss

Use of intraoperative fluids (crystalloid, colloid, blood products)

TOXICITIES/SIDE EFFECTS

Various symptoms have been associated with the administration of pregabalin in the perioperative setting. The risk of serious adverse events in this use of pregabalin is low [25] and the potential benefits of this treatment may outweigh the risks. This will be recorded in the PACU side effect and PACU nursing questionnaires.

Surgical complications will be assessed prospectively and retrospectively and reviewed using the institutional standard for complications reporting for all surgical patients as followed by the Department of Surgery. Standardized graded complications and adverse effects at UM utilize the five-point modified Clavien-Dindo system. Grade I include complications requiring monitoring but no intervention; Grade II requires bedside or medical treatment; Grade III constitute adverse events requiring surgical or procedural intervention with return to normal functioning; Grade IV includes disabling, life-threatening complications with resulting functional loss and grade V is death of the patient. This is a modification of the Clavien-Dindo system for reporting complications with defined, categorized and classified events that will be segregated into time periods of ≤ 30 days, 31-90 days and > 90 days after surgery and includes medication complications following NCI CTCAE version 5 guidelines.

CRITERIA FOR THERAPEUTIC RESPONSE/OUTCOME ASSESSMENT

If the surgery is aborted for any reason before placement of a ureteral stent, the patient will be removed from the study and replaced. Based on past experience these issues are rare events.

The intraoperative period is defined as the period from anesthesia induction to the extubation of the trachea. The surgical time is determined from the incision to the final skin closure.

The postoperative period is defined as the period from the extubation to various study endpoints.

Blood loss is defined as the estimate accounted from the suction device and absorptive sponges during the procedure, as described and agreed upon by the surgeon, anesthesiologist, circulating nurse, and surgical technician as covered by institutional guidelines.

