The patient's pain will be evaluated with a visual analogue scale of pain [27]. This may either be done digitally or by paper [28].

A validated questionnaire (the Ureteral Stent Symptom Questionnaire [USSQ]) exists to evaluate symptoms of ureteral stents and their effects of quality of life [1]. This will be used to evaluate how patients tolerate the stents.

Patient satisfaction will be assessed at PACU discharge as part of the patient's PACU discharge questionnaire. Similarly, satisfaction will be evaluated via questionnaires at subsequent time points.

CRITERIA FOR REMOVAL FROM STUDY

Patients will be withdrawn from the study if they express a desire to do so, if it is determined to be in the patient's best interest to do so, or if they do not undergo initiation of their surgical procedure as stipulated previously. For this pilot, if a patient fails to receive the study drug, they will be withdrawn from the study and analysis of this failure will be undertaken.

BIOSTATISTICS

Sample Size

The primary purpose of this study is to evaluate safety and feasibility of studying perioperative pregabalin at our institution, with the aim of performing a randomized, placebo-controlled, double-blinded study in the future. 10 patients will complete the study. This is a number that will allow for evaluation of potential serious side effects and feasibility. This number is also small enough that it will not waste resources or delay the future larger study. We estimate that 20 patients will need to be enrolled so that 10 will complete the study. This number of patients will be enrolled over 3 months.

Analysis

Descriptive statistics will be used in reporting patient outcomes in this pilot study. As there is no control group, significance tests will not be performed. Several questionnaires have narrative components which will be compiled and analyzed in a systematic method.

Proposed Analyses

Pre-specified parameters to be reported include the following:

- Serious adverse events
- All adverse events
- Proportion of enrolled patients completing the study
- Adverse events related to study drug
- Ureteral Stent Related Symptom Questionnaire (USSQ) [1] score at 3 days post op
- Monitored prescribing of narcotic pain medication
- Number of patients taking narcotic pain medication at several time points
- Oral morphine equivalents the patient has used at several time points
- Number of unplanned contacts between the patient and the healthcare system within 30 days

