
- Yes
- No

On what side was ureteroscopy performed?

- Right
- Left
- Bilateral
- None

Was the patient extubated in the OR?

- Yes
- No

What was the planned disposition for the patient?

[figure not shown]
- Home from PACU
- Floor
- ICU

Pacu Discharge

At one hour post op: How much pain is the patient in?

No pain

Most pain

(Place a mark on the scale above)

Where is the patient going after PACU discharge?

- Home from PACU
- Floor
- ICU

How long was it (in minutes) from when the patient arrived in the PACU until they went home?

Please indicate if the patient experienced any of the following since surgery. A check indicates that the patient did experience this adverse event.

	Yes
Dizziness	
Vertigo	
Incoordination	
Balance disorder	
Ataxia	
Diplopia	
Blurred vision	
Amblyopia	
Tremor	
Somnolence	
Confusional state	
Disturbance of attention	
Thinking abnormality	
Euphoria	
Edema	
Peripheral edema	
Asthenia	
Fatigue	
Dry mouth	
Constipation	
Amnesia	
Back pain	
Contusion	
Depersonalization	
Diarrhea	
Fall	
Headache	
Hyperhidrosis	
Increased appetite	
Infection	
Memory impairment	
Nausea	
Nervousness	
Neuropathy	
Pain	
Paresthesia	
Sinusitis	

Upper RTI

Vomiting

What are the patient's expectations regarding post-operative pain?

- There will be minimal pain regardless of treatment
- The pain regimen being given for discharge will be sufficient
- More pain medication will be required

What pain control does the patient believe they will need in addition?

- Opioid pain medication
- Non-opioid pain medication only

Aldrete

Time to Aldrete 9 or 10:

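### The only printed adverse event checklist counts from surgery, not from the pregabalin dose about an hour earlier, and does not record whether a symptom was present before the dose

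*Protocol*

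**What the plan says.** The protocol's Primary Endpoints list begins with "Adverse events related to study drug". Its later section on toxicities and side effects, under Protection of Human Subjects, promises that every potential side effect will be captured by questionnaire.

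Under Pre-op standardized care, the single oral dose is given "with a sip of water approximately one hour before surgery". In Appendix 1, the Pacu Discharge form introduces its list of events with "Please indicate if the patient experienced any of the following since surgery", followed by one Yes box per item.

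For symptoms attributed to pregabalin, the Toxicities/Side Effects section says "This will be recorded in the PACU side effect and PACU nursing questionnaires". The same section describes a graded review of surgical complications, prospective and retrospective, which "includes medication complications following NCI CTCAE version 5 guidelines".

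Proposed Analyses lists "Adverse events related to study drug" and "All adverse events" as separate outputs. The SAP, a single paragraph, reports proportions with possible adverse effects. It names no source form, time window or rule for relatedness.

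**The concern.** A safety endpoint for a drug should be observed from the moment the drug is taken. Here the checklist starts its clock later, at surgery. An effect that appears in the preoperative area and has gone by the time surgery starts is, on a literal reading, not to be ticked.

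The second weakness works in the other direction. Stone disease is a typical indication for the procedure, so some patients may arrive with pain or nausea. If the symptom continues after surgery, the box is ticked and looks the same as an effect that began after the dose.

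One flaw lowers the count and the other raises it. Safety is one of the two stated purposes of the pilot, and its results are meant to inform a randomised trial, so a count with an unclear window and no baseline would be carried forward.

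**Working it through.** This is mainly a comparison of texts. Every printed instrument in Appendices 1 and 3 was read against the dosing time, the evaluation schedule, the primary endpoints and the SAP.

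1. **Window.** The dose comes about one hour before surgery, and the checklist period begins at surgery. About one hour after dosing therefore lies outside the wording. It is also unclear whether the intraoperative period counts. An effect that persists into the PACU can still be ticked, so what is lost is limited to non-serious effects that both start and resolve before surgery.

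2. **Pre-dose status.** The checklist has 39 items by count, among them pain, back pain and nausea. None has a field for onset, for presence before the dose, or for relatedness. The Screening questionnaire and the Baseline Surgery form contain no current-symptom item that could serve as a baseline. The routine history described under Pretreatment Evaluation may help in part, but no form links it to the checklist.

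3. **Form names.** Toxicities/Side Effects refers to two PACU questionnaires, one for side effects and one for nursing. No printed form has either title. The closest are Pacu Discharge, which carries the checklist, and Evaluation of trial PACU nurse, which apart from the date holds only an open request for feedback on the study.

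4. **Soon after discharge.** The schedule places the Early patient questionnaire at days 3 and 7. It asks about satisfaction, stent status and pain medication taken, and has no side effect item. The USSQ, also at day 3, is not printed for copyright reasons; the protocol describes it as a stent symptom measure, and only three index scores are entered in REDCap. Non-serious effects in these days therefore depend on the patient volunteering them or on the staff-driven complication review.

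5. **Scale.** The protocol states: "We estimate that 20 patients will need to be enrolled so that 10 will complete the study". The implied completion is 10/20 = 50%, and 10/0.50 = 20 returns the plan's own figure. One patient wrongly counted or missed on an item moves its proportion by 1/10 = 10 percentage points among 10 completers, or 1/20 = 5 points if all 20 enrolled are dosed. This is the weight of one patient, not an estimate of how many are affected. The documents give no event rate or capture rate from which such an estimate could be made.

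**The case against.** The strongest reply is that the gap is small. The excluded interval is about an hour, patients are closely monitored around surgery, and serious events must be brought to the study staff at once. The Background section calls the principal side effects temporary. Nothing in the documents suggests that brief effects confined to the preoperative area are common. No test or threshold depends on the count, and in an uncontrolled descriptive pilot it is fair for the SAP to speak of possible effects. All of this stands and limits the size of the point. It does not justify a window that opens after the dose, or a tick that cannot be read as new.

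A reader might infer more: that since none of the six scheduled time points after PACU discharge (days 3, 7, 30 and 90, 6 months and 1 year) has a printed question specifically on drug side effects, drug events after discharge go unrecorded. The tally is literally correct, but the documents do not support the inference. A single dose with effects described as temporary gives little reason to count day 30 to 1 year as missed opportunities. Other routes also exist:

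- the graded review covers medication complications and its periods extend beyond 90 days;
- the Unanticipated Contact form prompts escalation of a serious event related to study medication;
- the day 30 staff form counts emergency visits and hospitalizations;
- the Late questionnaire and Evaluation of trial have open questions;
- Appendix 4 tells patients to call about any issue with the procedure or with taking part.

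What remains is narrower: non-serious effects in the first days are not asked about directly.

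Nor does the mismatch in form names show that a side effect form is missing. The names may be other titles for printed forms, or may refer to forms not printed.

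**Conclusion.** The point holds in a limited form and should be fixed. The printed checklist omits part of the post-dose period for a primary endpoint and cannot distinguish new from pre-existing symptoms. The form names need reconciling, and direct questioning about side effects soon after discharge is thin.

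The size cannot be quantified. Because one flaw removes events and the other adds them, even the net direction of error is unknown. A reader might conclude that the pilot will understate harm or that serious events will be missed; the documents support neither.

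The conclusion assumes that the printed forms are the ones in use, that staff follow the stem literally, and that the unseen USSQ is the stent symptom measure the protocol describes.

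**What to change.** - Change the checklist stem to 'since taking the study pregabalin dose'.
- Give each item three answers: No; Yes, new or worse since the dose; Yes, present before the dose and no worse.
- In the SAP, report new or worsened possible adverse effects per patient dosed. State that denominator explicitly, because the protocol removes and replaces patients whose surgery is aborted before stent placement, and they may already have been dosed.
- Reconcile the questionnaire names in Toxicities/Side Effects with the printed instruments, or add the named forms to Appendix 1.

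The cost is a REDCap edit, one or two SAP sentences and a minor amendment, with no added visits or procedures.

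Optional: add one short item to the existing day 3 Early questionnaire asking about new or worse side effects since PACU discharge. Report it separately and descriptively, because the other drugs given confound it and it cannot support attribution. The burden is small but not nil: the same form is used at day 7, so it would need branching or a split, and only half of those enrolled are expected to complete. Repeating all 39 items at day 3 would add burden out of proportion to what the answers could show.

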interventions are performed yearly in the US on working age adults [5], thereby, at least 120,000 ureteroscopies are. There are several other indications for ureteroscopy, including diagnosis of structural anomaly and diagnosis and management of ureteral and renal pelvic tumors.

Depending on the specifics of the procedure, it may be advisable to place a ureteral stent intraoperatively [6]. The most commonly used variety of stent is the double J stent [7], which has long been known to cause post-operative pain in around 80% of patients, as well as irritative symptoms in a sizeable portion [8, 9]. A validated questionnaire (the Ureteral Stent Symptom Questionnaire [USSQ]) exists to evaluate symptoms of ureteral stents and their effects of quality of life [1].

Alpha-blockers decrease ureteral stent discomfort when compared to placebo [10, 11]. Anti-muscarinic medications (specifically tolteridine) have also been shown to be helpful with stent related discomfort independently, or in addition to alpha blockade [12], though the evidence is mixed [13]. A recent systematic review failed to find any studies of other medications for stent related discomfort that met inclusion criteria [14]. Subsequently, a well-designed study demonstrated the utility of mirabegron for indwelling stent symptoms [15].

Recent guidelines recommend the use of multimodal treatment strategies in the management of postoperative pain [16]. In several contexts gabapentin or pregabalin have been shown to be a beneficial part of such a strategy. For example, in percutaneous nephrolithotomy, a randomized, placebo-controlled, double-blind study demonstrated that a single dose of 600mg of oral gabapentin 1 hour before surgery significantly decreased catheter-related bladder discomfort, number of patients requiring opioid pain relief, and amount of opioid pain relief when used [17]. Similarly, outside urology, several well-designed trials demonstrate the positive effects of perioperative pregabalin or gabapentin in the elective, outpatient surgery setting [18-20]. Several reviews and meta analyses have also supported the use of perioperative gabapentin or pregabalin in various settings [21-24]. The principal side effects of pregabalin are temporary cognition/coordination changes, with a very low risk of serious side effects [25]. No well-constructed studies to date have examined the perioperative use of gabapentinoids in post-ureteroscopy ureteral stent related symptoms.

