A standardized post-operative regimen will be used, consisting of a single belladonna & opium suppository, a single dose of ketorolac 30mg IV, and ondansetron 4mg IV. A single dose of hydrocodone 5mg with acetaminophen 325mg PO will be available PRN pain.

To qualify for discharge from the PACU, all patients will have had to have met a standardized set of discharge criteria. They will have to have ambulated, voided, tolerated PO intake, and have pain subjectively adequately controlled.

On PACU discharge, patients will be given a prescription for 20 tablets of 50mg diclofenac, 20 tablets of acetaminophen 650mg to be taken on a scheduled basis every 6 hours, and mirabegron 50mg once daily PO to be taken until stent removal [15]. There is no universal standard of care discharge regimen after ureteroscopy, but a similar one to this has been shown to be safe and effective [26]. Patients will receive a standardized sheet of return precautions. They will receive packets of questionnaires to be completed along with pre-addressed and pre-stamped envelopes. They will be instructed to only seek pain medication from the urology team for the next month. Should they have need for further pain medication, patients will be instructed to call the clinic [see supplementary material]. They will be offered their choice of another 3 days of NSAID or oxycodone 5mg q6h PRN pain 6 tablets. Further treatment will be at provider discretion. The clinic staff will be instructed to record these prescriptions.

THERAPEUTIC AND DIAGNOSTIC AGENTS

Pregabalin is an oral agent approved for use in fibromyalgia and neuropathic pain. A single dose of 300mg PO will be given to all patients.

RECRUITMENT PLAN

Patients will be recruited from the practice of [name] in the Division of Urology, Department of Surgery. The study will be introduced to every eligible patient scheduled for ureteroscopy with stent placement by the participating consenting physicians from the Department of Surgery-Urology Division and a written consent obtained prior to surgery by the consenting research personnel. Candidate subjects will be provided time to consider the study, to read the informed consent document at their convenience, and discuss the study with family and others, as desired. It will be clearly indicated that non-enrollment in the study will not negatively affect the patient's care.

PRETREATMENT EVALUATION

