STATISTICAL ANALYSIS PLAN

Project Title: Perioperative pregabalin as part of a multimodal treatment plan for pain after

ureteroscopy with stent placement: a pilot

IRB Number: 2013680 Version Number: 1.1 Version Date: 11/20/2019

Principal Investigator: [name]

Funding Source: Departmental Clinical Trial Phase: Not Phased

Clinicaltrials.gov Number: NCT03927781 Study Drug/Study Device: Pregabalin

Principal Investigator	[name]	Department of Surgery Urology
		Division
Co-Investigator	[name]	Department of Surgery Urology Division
Consenting Professional(s)	Donartment of Surgery	DIVISION
Consenting Professional(s)	Department of Surgery-	
Department	Urology	

University of Missouri University Hospital Department of Surgery Urology Division [name] Descriptive statistics (counts, proportions, medians) will be used to describe all data. We will describe the demographic information of the patients enrolled and the number of patients approached to meet full enrollment. We will assess the proportion who anticipated needing opioid pain medication, who appropriately received pregabalin, who received opioid pain medication at discharge, who had emergency room visits or hospitalizations in the first 30 post-operative days, and who received opioid prescriptions within the first 30 post-operative days. We will describe the number of oral morphine equivalents prescribed. We will include median USSQ scores. We will describe proportions reporting possible adverse effects and pain level reported. All analyses will be performed in R version 3.5.1. There will be no statistical tests performed.

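### The primary endpoint of drug-related adverse events has no planned data to separate it from all adverse events

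*Protocol*

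**What the plan says.** The protocol lists "Adverse events related to study drug" first among its Primary Endpoints. Under Proposed Analyses the same item appears apart from "All adverse events", so the plan treats them as two results.

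On collection, the Toxicities/Side Effects section says of pregabalin-associated symptoms: "This will be recorded in the PACU side effect and PACU nursing questionnaires". Appendix 1 has no forms under those two titles. The only adverse event list there is on the Pacu Discharge form, which I take to be the instrument meant. Its instruction reads: "Please indicate if the patient experienced any of the following since surgery. A check indicates that the patient did experience this adverse event".

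On timing, the pre-operative care section says "all patients will be given a single dose of pregabalin 300 mg PO with a sip of water approximately one hour before surgery".

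On analysis, the SAP says: "We will describe proportions reporting possible adverse effects and pain level reported". It plans no statistical tests, and there is no control group.

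**The concern.** To report drug-related events separately from all events, something has to decide which events belong in the smaller set. In a single-arm study the usual means are the patient's state before dosing and a recorded judgement of relatedness. The plan has neither.

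Several checklist items can have other causes in these patients: their existing stone or ureteral disease, the new stent, general anaesthesia (Surgical Plan), and the standard post-operative drugs, "consisting of a single belladonna & opium suppository, a single dose of ketorolac 30mg IV, and ondansetron 4mg IV". Pain, back pain, nausea, vomiting, somnolence, dry mouth and constipation are all on the list.

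At stake is the pilot's safety conclusion. An all-cause figure could make the drug look worse than it is, or could be dismissed as non-specific. The planned randomised trial could also inherit the same forms.

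**Working it through.** The documents give no adverse event rate or precision target, so there is no plan figure to reproduce. The check compares the forms, then shows with assumed rates what the checklist can identify.

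**Step 1. What each Appendix 1 form records**

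| Form | Content bearing on safety | Relatedness to pregabalin |
|---|---|---|
| Screening; Baseline Surgery | Eligibility, identity, indication, side, expected pain control; no current symptoms | None |
| Pacu Discharge | One-hour pain scale; 39 yes-only boxes; no onset time or severity | None |
| Early patient questionnaire | Satisfaction, stent status, analgesics taken | None |
| 30 Days Post Op Study | Emergency visits and hospitalisations, in total and related to the ureteroscopy | None |
| Unanticipated Contact | Relation to stent discomfort | Only an example in the prompt to alert study physicians; not a recorded field |
| Late patient questionnaire | Free-text issue linked to the procedure | None |

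The forms therefore do ask about relation to the stent and to the procedure. None records relation to the study drug. The protocol names modified Clavien-Dindo and CTCAE version 5, which classify and grade events, but it gives no assessor or rule for causality.

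**Step 2. The window**

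The order is dose, about one hour, surgery, PACU. The checklist asks about the time from surgery onward. A symptom that starts and ends in the hour after the dose is not asked for. A symptom present before the dose and still present in PACU can be ticked like a new one.

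**Step 3. What a ticked proportion can show**

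For one item, let b be the risk from all other causes and d the risk caused by the drug, taken as independent. The expected proportion of patients ticking it is

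r = 1 − (1 − b)(1 − d).

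The values of b and d below are assumptions; the documents give none for the PACU.

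| b | d = 0 | d = 0.10 | d = 0.30 |
|---|---|---|---|
| 0.10 | 10% | 19% | 37% |
| 0.30 | 30% | 37% | 51% |
| 0.50 | 50% | 55% | 65% |

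The value 37% appears twice: 1 − 0.90 × 0.70 = 0.37 and 1 − 0.70 × 0.90 = 0.37. It would also arise with b = 0.37 and d = 0. One observed proportion is thus compatible with a drug-caused risk of 0, 10% or 30%. This is a matter of identification, so it does not depend on whether 10 or 20 patients fill in the form.

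**Step 4. If the items were pooled**

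The SAP does not say that it will report patients with at least one tick. If it did, and each of the 39 items had an independent background rate p, the proportion with a tick and no drug effect would be 1 − (1 − p)^39. That is 32% for p = 1%, 55% for 2% and 86% for 5%.

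**Step 5. What a pre-dose checklist would remove**

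Split b into a pre-existing part b0 and a part b1 that starts after the dose. All ticks: r = 1 − (1 − b0)(1 − b1)(1 − d). Among patients without the symptom before dosing: 1 − (1 − b1)(1 − d). The baseline removes b0 only. Stent, anaesthetic and suppository effects sit in b1 and remain.

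**The case against.** The strongest reply is that the protocol already keeps the two results apart, and that with so few patients the investigators can attribute events case by case. CTCAE grading is named, serious events go to the IRB under an institutional procedure, and an institutional monitoring plan is cited. The last two documents are not available here, so they cannot be assumed to contain or to lack causality rules. This stands against any claim that the endpoint is unobtainable. It does not fill the gap in the forms: such attribution would be open-label, unrecorded and made afterwards, and a pre-dose state that was never recorded cannot be recovered later.

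A second reply is that only a control group truly separates drug from background, and that the pilot is meant to lead to a placebo-controlled trial. This also stands. Step 5 shows that a baseline leaves every cause arising after the dose.

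A reader might infer several stronger things that the documents do not support:

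- That every tick is counted as a pregabalin effect. No text says so, and the SAP's wording on possible adverse effects does not name the drug.
- That the checklist has no time frame. It has a window, from surgery to PACU discharge; what it lacks is onset time and the interval after dosing.
- That about 8 of 10 patients would tick Pain regardless of the drug, because the Background says of the double J stent "which has long been known to cause post-operative pain in around 80% of patients". That is a general figure for stents, not a PACU rate after anaesthesia and analgesics. Pain is also the item least likely to be read as toxicity of an analgesic, and it has its own scale on the same form.

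**Conclusion.** The concern holds in limited form. The plan names a primary endpoint that needs attribution, but it collects neither the pre-dose state nor relatedness, and it states no rule for assigning it. As written, the checklist yields all-cause symptom proportions from surgery to PACU discharge. A drug-related figure could be produced only by judgement that is neither pre-specified nor recorded.

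No numerical bias can be given, because the documents supply no PACU background rates. The table in Step 3 is an illustration with assumed, independent risks. The conclusion also assumes that the Pacu Discharge checklist is the questionnaire meant in the Toxicities/Side Effects section. Items with few competing causes, such as diplopia, are less affected than nausea or somnolence.

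The point should be acted on: it concerns the first-listed primary endpoint, and the remedy is cheap.

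**What to change.** 1. Give the same checklist once before the pregabalin dose, for example on the Baseline Surgery form, so that pre-existing symptoms can be removed.
2. On the Pacu Discharge form, start the window at the study dose. For each ticked item add: new or worse than before the dose (yes/no), a CTCAE grade, and a relatedness judgement by a study investigator with the likely alternative cause (existing disease, stent or procedure, anaesthetic, suppository or other analgesic).
3. In the SAP, define the primary endpoint as new or worsened events judged at least possibly related to pregabalin. Report all-cause events item by item alongside it.

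The cost is a few minutes before surgery, a few added REDCap fields and a sentence or two in the SAP. Sample size and care do not change. Relatedness in an open-label study remains a judgement, which is why the all-cause figures should stay beside it. The report should also say that drug effects and other effects starting after the dose cannot be fully separated without a control group.
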